8.1.1. Primary Analysis

For Period 1 analysis, Spearman correlation coefficient and its 95% confidence interval will be calculated for the correlation analysis between change from baseline in CFS score at visit X and SANDE symptoms score at each visit X+i in period 1 using the FAS Period 1 population.

The primary efficacy endpoint analysis result will be presented graphically by plotting Spearman correlation coefficients calculated at each visit. Spearman correlation coefficients will be plotted for the timepoints where more than 2 lagtime correlations are calculated. The plots will have x-axis to show lags, i, and y-axis to show Spearman correlation coefficients as shown in Figure 2, which is for X = Month 3.

Figure 2. A Sample Plot of Correlation between Change from Baseline in CFS Score at Visit X vs. Change from Baseline in SANDE Score at Visit X + i

Spearman Correlation Coefficients Calculated at Month 3

Interpretation of the results from graphical analysis:

- o If any individual graph shows a "bump" or a plateau at any lag > 0 point, as shown in Figure 2, it would be considered as an indication of existence of a lagged symptom response for CFS score at that particular visit X.
- o If there are at least half (50%) of the graphs show lagged symptom responses, we would conclude that dry eye symptoms (measured by SANDE questionnaire) show lagged response improvement in comparison to dry eye sign improvement.

For Period 2 analysis, Spearman correlation coefficient between change from baseline in CFS score at visit X and SANDE symptoms score at each visit X+i, its 95% confidence interval will be calculated by treatment group. The analysis will be based on the FAS Period 2 population.

For long term efficacy, the Entire Study analysis will be performed by repeating the Period 1 analysis for the entire 3 year duration using the FAS Entire Study population.

The analysis details are shown in Table 4 by study period.

Table 4 Analysis of Correlation between Change from Reference Point in CFS Score at Visit X and Change from Reference Point in SANDE Symptom Score at Visit X + i

Study Period / Analysis Population	Reference Point	Visit X	Visit X + i
Period 1 FAS Period 1 subjects	Baseline	Month 3*	Month 3, Month 6, Month 9, Month 12
		Month 6*	Month 6, Month 9, Month 12
		Month 9	Month 9, Month 12
		Month 12	Month 12
Period 2 FAS Period 2 subjects (by treatment arm)	Month 12	Month 15*	Month 15, Month 18, Month 21, Month 24, Month 27, Month 30, Month 33, Month 36
		Month 18*	Month 18, Month 21, Month 24, Month 27, Month 30, Month 33, Month 36
		Month 21*	Month 21, Month 24, Month 27, Month 30, Month 33, Month 36
		Month 24*	Month 24, Month 27, Month 30, Month 33, Month 36
		Month 27*	Month 27, Month 30, Month 33, Month 36
		Month 30*	Month 30, Month 33, Month 36
		Month 33	Month 33, Month 36
		Month 36	Month 36

Study Period / Analysis Population	Reference Point	Visit X	Visit X + i
Entire Study (Period 1 + Period 2) FAS Entire Study subjects	Baseline	Month 3*	Month 3, Month 6, Month 9, Month 12, Month 15, Month 18, Month 21, Month 24, Month 27, Month 30, Month 33, Month 36
		Month 6*	Month 6, Month 9, Month 12, Month 15, Month 18, Month 21, Month 24, Month 27, Month 30, Month 33, Month 36
		Month 27*	Month 27, Month 30, Month 33, Month 36
		Month 30*	Month 30, Month 33, Month 36
		Month 33	Month 33, Month 36
		Month 36	Month 36

^{*} Spearman correlation coefficients will be plotted

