4.2.2. Baseline Score

The *baseline score* is the observed measurement at Baseline (Day 1).

In addition, for subjects who got randomized in Period 2, the observed measurements made at Month 12 Visit will be used as baseline scores for Period 2. If a Month 12 measurement is

missing, the last observed measurement or derived score prior to the first dose of the Period 2 double-masked study treatment will be used to impute the baseline score for Period 2.

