4.2.3. Change from a Reference Point

For Period 1 and Entire Study analyses, the change from baseline at a post-baseline visit will be derived as:

```
Change = (Score at the Post-Baseline Visit) – (Baseline Score)
```

For Period 2 analyses, change from Month 12 will be the change used in the analyses.

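### The primary lag statistic can show a plateau or bump with no symptom delay, so the SAP's reading rule can often conclude a lag when there is none

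*SAP*

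**What the plan says.** Estimating any lag time to symptom improvement is part of the first primary objective (Protocol 5.1, SAP 2.1). SAP 8.1.1 specifies a Spearman "correlation analysis between change from baseline in CFS score at visit X and SANDE symptoms score at each visit X+i in period 1". The titles of Figure 2 and Table 4 show that SANDE is a change as well: "Change from Reference Point in SANDE Symptom Score at Visit X + i". The reference is Day 1 for Period 1 and Entire Study. For Period 2, SAP 4.2.3 states: "For Period 2 analyses, change from Month 12 will be the change used in the analyses".

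On plotting, the SAP says: "Spearman correlation coefficients will be plotted for the timepoints where more than 2 lagtime correlations are calculated". In Period 1 this gives two graphs: X = Month 3 with four points and X = Month 6 with three. If a graph shows a bump "or a plateau at any lag > 0 point, as shown in Figure 2", then "it would be considered as an indication of existence of a lagged symptom response for CFS score at that particular visit X". The study-level rule begins "If there are at least half (50%) of the graphs show lagged symptom responses" and ends in the conclusion that symptoms respond with a lag. In Period 1, one graph is therefore enough. The rule stands with the Period 1 text, and the Entire Study analysis repeats the Period 1 analysis. Period 2 has six starred rows per arm, and the text does not say separately how they are read.

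The text gives no numeric definition of bump or plateau, no comparison with lag 0, no picture of the curve expected without delay, and no adjustment for reference scores or for CFS at X+i. The sensitivity analysis (SAP 8.1.2) repeats the same statistic in the per-protocol sets.

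**The concern.** A lag statistic should separate two situations: symptoms that follow the sign at once, and symptoms that follow it later. Two features of this one blur them.

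- **Shared reference visit.** One change subtracts reference CFS and the other reference SANDE. Any association between those two scores enters the correlation at every lag.
- **Persistence of CFS.** A patient with better CFS at X tends to have better CFS at X+i, and that later CFS acts on SANDE at X+i without delay. Correlation at later lags then reflects the course of the sign, not a delay in symptoms.

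At stake is a stated conclusion for a primary objective. Protocol 4.2 already reads a rising correlation of changes in a previous trial as support for a lag, while calling it inconclusive.

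**Working it through.** **Inputs.** From the documents: 350 enrolled (SAP 3.3, used as the number analysed, attrition ignored), Day 1 CFS of 3 to 5 (Protocol 7.1), the modified Oxford grades, and the visits and references in Table 4. Not in the documents: the correlation of CFS between visits and the strength of the sign-symptom link. Both were varied.

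The plan states no figure for the lag rule. Its nearest figure is 80% power for a CFS difference of 0.4 (147 vs 98, SD 1.10). It reproduces, with two-sided 0.05 assumed: 1.10 × √(1/147 + 1/98) = 0.143; 0.4/0.143 = 2.79; 2.79 − 1.96 = 0.83, so 79.6%. This does not bear on the lag. It only gives a scale for CFS variability; the simulated SD of CFS change at Month 12 was 0.92 to 1.34.

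**Algebra without delay.** Let S(t) = βC(t) + patient effect + noise. The patient effect cancels in the changes, so

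Cov[C(X) − C(0), S(X+i) − S(0)] = β Cov[C(X) − C(0), C(X+i) − C(0)].

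The expected curve therefore traces how CFS changes relate to later CFS changes.

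- *Constant between-visit correlation ρ, equal variance σ²:* 2βσ²(1 − ρ) at lag 0 and βσ²(1 − ρ) at every later lag. This is a flat line at half the lag-0 value. A simulated same-visit link of r = 0.3 gave 0.28, then 0.14 at each later lag.
- *Response growing with time, C(t) − C(0) = t·g + e(t) − e(0):* for i > 0 the covariance is β[X(X+i)Var(g) + Var(e(0))], which rises with i.
- *AR(1), ρ = 0.5, X = first post-baseline visit:* ρ^i − ρ^X − ρ^(X+i) + 1 gives 1, 0.75, 0.625, 0.5625. This declines steadily.

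**Simulation without delay.** Curves come from 400,000 simulated patients; rates come from 1,500 trials of 350 and refer to at least one of the two Period 1 graphs. Working definitions: a rise is any value above the one at the previous lag; a plateau is two successive points at lags > 0 within 0.05.

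| CFS pattern | Month 3 curve, lags 0–3 | Rise | Later lag above lag 0 | Rise or plateau |
|---|---|---|---|---|
| Independent visits | 0.50, 0.18, 0.18, 0.18 | 90% | 0% | 100% |
| Constant 0.3 | 0.46, 0.18, 0.18, 0.18 | 91% | 0% | 100% |
| Constant 0.6 | 0.53, 0.23, 0.23, 0.23 | 90% | 0% | 100% |
| AR(1) 0.5 | 0.41, 0.24, 0.18, 0.14 | 41% | 0% | 88% |
| AR(1) 0.8 | 0.32, 0.22, 0.19, 0.16 | 59% | 8% | 96% |
| Growing, stronger link | 0.53, 0.39, 0.42, 0.44 | 99% | 4% | 100% |
| Growing, weak link | 0.20, 0.16, 0.18, 0.19 | 99% | 72% | 100% |
| No sign-symptom link | 0, 0, 0, 0 | 99% | 92% | 100% |

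With independent visits, raw scores without the Day 1 subtraction give 0.48, 0, 0, 0, so that plateau comes only from Day 1. With constant correlation 0.6 the raw scores are also flat (0.28), and with growing response they also rise (0.37 to 0.42), so there persistence alone is enough. The 95% half-width of a correlation near zero at N = 350 is about 1.96/√347 = 0.105, large against the differences within a curve.

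Other assumed values with 300 patients gave a rise in 29% to 100% of no-delay trials. Under growing response they gave a later lag at or above lag 0 in 74% to 94%.

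**Partial correlations (X = Month 3).** Given both Day 1 scores and CFS at X+i, the values at lags 1 to 3 were −0.002 to 0.009 in six no-delay cases (constant 0.3 and no link not rerun). With a true one-visit delay, the lag-1 value was 0.43 to 0.47 and lag 0 was about 0. Partialling out the Day 1 scores alone is not enough: about 0.20 remained with constant correlation 0.6, and 0.37 to 0.43 with growing response and the stronger link.

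**The case against.** **The visual rule, not the statistic, is the main fault in many settings.** Largely true. In the table, asking a later raw correlation to exceed lag 0 gives 0% to 8% false signals wherever there is a link, apart from growing response with a weak link (72%). It found a true one-visit delay in 100% of trials. So it would be wrong to infer that no cut-off on the raw curve could help. It fails when response grows over the year, a course that cannot be ruled out for a 12-month open-label period.

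**A plateau below lag 0 may not count.** Figure 2 is missing from the text examined, so this cannot be settled here. The rise-or-plateau rates depend on the working definition. The rise-only rates do not depend on the plateau definition.

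**The shape is not inevitable.** A reader might infer that the statistic always shows a plateau or bump, and that Day 1 subtraction is the sole cause. Neither holds. AR(1) curves decline, persistence produces the shape on its own, and the Period 2 reference is Month 12.

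**The study is exploratory.** Protocol 13.1.2 sets no hypotheses, and the coefficients with their intervals are reported anyway. That limits the harm to the interpretive rule, but the rule states a conclusion on a primary objective.

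**The partial-correlation rule has its own weaknesses.** Later lags are adjusted for more than lag 0 is, which favours lag 0. In one growing-response model (300 patients), a true 3-month lag gave 0.32 at lag 0 and 0.30 at lag 1 in the Month 6 graph, which detected it in 41% of trials. A half-immediate, half-3-month response was detected in 26% (either graph). This stands and must be stated.

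**Conclusion.** The concern holds in this form: the raw statistic can show a plateau or bump without delay, and the rule attached to it can often declare a lag when there is none.

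The size is a range. For a rise in at least one of the two Period 1 graphs, it is 29% to 100% of no-delay trials across all assumed values. For a later lag reaching or exceeding lag 0, it is near 0% in most settings with a link, but 4% to 94% under growing response. A reader might want one headline rate, and one illustrative growing-response model with about 300 patients gives 97%. That figure belongs to that model only. The documents give neither the between-visit CFS correlation nor the sign-symptom correlation, and Protocol 4.2 describes the latter as usually poor.

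Nor do the documents support the inference that any lag found would be false. A true delay also produces a signal; the planned rule does not separate the two.

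**What to change.** In SAP 8.1.1 and Table 4, with an entry in section 10:

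1. Keep the raw Spearman curves and intervals as the descriptive protocol endpoint.
2. Base the lag conclusion on partial Spearman correlations (PROC CORR with SPEARMAN and a PARTIAL statement). At i = 0, partial out the reference-visit CFS and SANDE: Day 1 for Period 1 and Entire Study, Month 12 for Period 2. For i > 0, also partial out CFS at X+i.
3. Conclude a lag only if a partial correlation at some i > 0 exceeds the one at lag 0, with a bootstrap confidence interval for the difference. Fix its level in advance, since Period 1 alone has 3 + 2 = 5 such comparisons.

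The interval is needed. Comparing point values alone gave 0% to 6% false signals in one set of simulations. In another it gave up to 14% under growing response and 29% under AR(1) with a weak link (against 81% on the raw curve). The same two sets still flagged true one- or two-visit delays in 96% to 100% of trials.

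The cost is SAP text, a documented change to how a primary endpoint is interpreted, and modest programming. No new data are needed, because CFS and SANDE are collected at every scheduled visit. State the downsides: patients without CFS at X+i drop from that point; CFS measurement error leaves a small residual (about 0.04 to 0.07 in simulation), so the comparison must be with lag 0 and not with zero; and the unequal conditioning sets lower sensitivity to short or mixed lags.

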1. INTRODUCTION

This statistical analysis plan (SAP) specifies the statistical methods and analyses to be implemented for the data collected from the IKERVIS PAES study within the scope of Santen's Protocol NVG14L127, "A phase IIIb, prospective, interventional, multicentre, three-year study to explore the long-term evolution of sign and symptoms, and occurrence of complications in dry eye disease subjects with severe keratitis receiving IKERVIS® (1mg/ml ciclosporin) eye drops". It applies to the study protocol Amendment 1 (version 3.0), dated 17-OCT-2018, and provides detailed instructions as to how each analysis will be performed.

Results obtained from the analyses specified in the final approved version of the SAP will become the basis of the clinical study report (CSR) for this protocol. Deviations from the final approved version of the SAP must be substantiated by sound statistical reasoning and documented in the CSR.

REVISION HISTORY FROM THE PREVIOUS VERSION (1.0):

- Reflected the latest version of MedDRA (Sec. 4.4)
- Updated the definitions of ocular surface complication (Sec. 4.4.1.1)
- Updated analysis set (Sec. 6)
- Added Sjogren patient population summary (Sec. 7 and 8)
- Added medical history summary for period 2 (Sec. 7.5)
- Added CFS shift table (Sec. 8.2)
- Added CFS complete resolution summary (CFS=0 at post BL) (Sec. 8.2)
- Added MMRM to estimate treatment difference for secondary endpoints (Sec. 8.2) and updated related section (Sec. 5.1 and 5.4)
- Clarified the duration of detail for ocular surface complication (Sec. 9.1)
- Added SAS sample code (Sec. 12)

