5. GENERAL CONSIDERATIONS

All measures will be summarized for Overall subjects in Period 1 and by treatment group in Period 2 as well as for the entire study descriptively. Continuous variables will be summarized using descriptive statistics such as number of observations (n), mean, standard deviation, median, minimum, and maximum. Categorical variables will be tabulated using frequency (n) and percent (%).

Unless otherwise specified, the following conventions on decimal places will be followed in reporting numerical results.

Statistic	Reporting Decimal Places
Range (Low Value, High Value)	Recorded decimal places
Mean, Median	Recorded value + 1 decimal places
Confidence interval, standard deviation, standard error	Recorded value + 2 decimal places
P-value	4 Decimal places (ex. 0.0021)

No statistical testing will be conducted for both the efficacy and safety measures for Period 1 in this study.

All data summary/analysis will be performed using SAS Version 9.4 or later. Individual data, including relevant derived variables, will be listed. Additional analyses not specified in this SAP may be conducted if deemed necessary and will be documented in the CSR.

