5.5. Interim Analysis

There is one interim analysis planned for this study. The purpose of the interim analysis is to present appropriate summary of data collected for the period 1. Interim analysis will be conducted once all subjects will have completed their Month 12 Visit or withdrawal visit.

Data cut criteria for this interim analysis is shown in Table 3.

Table 3 Data Cut Plan for Interim Analysis

Analysis Data	Data Example	Data Cut Criteria
Visit Data	IOP, TBUT, DEQS, etc. that are collected on visit date	Data collected at Month 12 or earlier will be included.
Non-visit Data	AE, medication, procedures, CSI, etc.	Incidents that happened up to the day of the first dose in Period 2 study drug will be included in the analysis.

Since the first 12 months of the study will be open-label study, no adjustment of alpha level and no Data Monitoring Committee will be needed for this study.

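### SAP 8.1.1 concludes a lagged symptom response from the shape of plots, with no numeric size and no use of the confidence intervals, so it can declare a lag when the true correlation is zero or flat

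*SAP*

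**What the plan says.** SAP 8.1.1 first sets up an ordinary estimation: "Spearman correlation coefficient and its 95% confidence interval will be calculated for the correlation analysis" of CFS change at visit X with SANDE change at visit X+i. On what is drawn: "Spearman correlation coefficients will be plotted for the timepoints where more than 2 lagtime correlations are calculated". Table 4 marks two such visits in Period 1 (Month 3 with lags 0 to 3, Month 6 with lags 0 to 2) and six per arm in Period 2.

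Two interpretation bullets follow. The first sets when a single plot counts. Besides a bump, it accepts the following: "or a plateau at any lag > 0 point, as shown in Figure 2, it would be considered as an indication of existence". Such a plot is taken to show a delayed response at that visit. The second gives the overall rule: "If there are at least half (50%) of the graphs show lagged symptom responses, we would conclude that dry eye symptoms" improve later than the sign does. The 50% is the only number in the rule.

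The bullets stand between the Period 1 and Period 2 text. The section later adds: "For long term efficacy, the Entire Study analysis will be performed by repeating the Period 1 analysis for the entire 3 year duration". It does not say over which set of plots the half is taken.

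SAP section 5 states: "No statistical testing will be conducted for both the efficacy and safety measures for Period 1 in this study". Protocol 13.1.2 sets no hypotheses for the primary and secondary endpoints, and SAP 5.4 calls the purpose exploratory.

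**The concern.** The correlation at each lag is an estimate with sampling error, and the rule looks for unevenness in a short run of such estimates. Chance alone makes them uneven. With no minimum height, no reference lag and no tolerance, two people can read the same plot differently, and the intervals that would show how much is noise play no part.

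Estimating the lag time is part of a primary objective (SAP 2.1), and Protocol 13.7 names lag time among the purposes of the interim analysis. Protocol 4.2 describes the agreement between symptoms and signs in these patients as poor, and the earlier evidence for a lag as inconclusive. A true correlation near zero is therefore plausible, and that is where the rule performs worst. The report could state a delayed symptom response that is only sampling variation.

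**Working it through.** The documents give no error rate or precision for this rule, so there is no stated figure to reproduce.

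**Inputs from the documents.** Period 1: 350 planned subjects (SAP 3.3), two plots with 4 and 3 coefficients (Table 4), 50% threshold (SAP 8.1.1). Period 2: 147 and 98 subjects, six plots per arm.

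**Assumptions.** Visit-to-visit autocorrelation of 0.4 to 0.9; ordinal CFS change; SANDE change that is unrelated to CFS (zero), equally related at all lags (flat), or related at the same visit and decaying with lag (concurrent). The half is counted within Period 1, so one of two plots is enough. All subjects have data.

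**Step 1, a simple bound on intuition.** If the coefficients within a plot are exchangeable, some later lag exceeds lag 0 with probability 3/4 (Month 3) and 2/3 (Month 6). Treating the plots as independent, P(at least one counts) = 1 - (1/4)(1/3) = 11/12 = 91.7%.

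**Step 2, the scale of noise.** The approximate 95% half-width of one coefficient near zero is 1.96/√(n-3): 1.96/√347 = 0.105 for n=350, 1.96/√144 = 0.163 for n=147, and 1.96/√95 = 0.201 for n=98. Bumps of 0.05 to 0.10 are no larger than the half-width of a single coefficient.

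**Step 3, simulation of the Period 1 rule with no true lag.**

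| Reading of the criterion | True correlation | Trials concluding a lag |
|---|---|---|
| Any coefficient above lag 0 | zero | 84-90% |
| At least 0.05 above lag 0 | zero | 16-61% |
| At least 0.10 above lag 0 | zero | 1-24% |
| Plateau: neighbouring coefficients within 0.02 | zero or flat | 76-98% |
| Plateau: neighbouring coefficients within 0.02 | concurrent, r=0.3, decaying | 46-85% |
| Narrow plateau: two neighbouring lags both more than 0.05 above lag 0 | zero or flat | 3-27% |

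For the bump readings, a flat correlation behaves much like zero. The ranges span the assumed autocorrelations.

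**Step 4, can the rule tell a lag from nothing?** A true one-visit lag of r=0.1 is declared in 91-98% of trials on the above-lag-0 reading, against 84-90% when there is no correlation at all.

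**Step 5, Period 2, if the rule is applied there** (3 of 6 plots, zero or flat correlation, between-visit correlation 0.5 or 0.7). With n=147: 98-99% for any bump, 60-77% above 0.05, 9-27% above 0.10. With n=98: 98-99%, 71-84% and 20-45%.

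**The case against.** Four points weigh on the other side.

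*The study is exploratory.* There are no hypotheses and no multiplicity plan, and every coefficient is reported with its interval, so a reader can see when the intervals cover zero. No treatment comparison or safety result depends on this rule. All of this stands and limits the harm. It does not rescue a rule that commits the report to a conclusion on part of a primary objective.

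*Figure 2 may define the shapes.* It is not visible in this copy. A reader might infer that any constant correlation is a plateau and so always meets the criterion without any delay. The documents do not establish that: the figure may intend a rise that then holds, which is a legitimate lag shape. On that narrower reading the false rate is about 3-27%, not 76-98%. The text itself takes no threshold from the figure, which it labels a sample.

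*One plot may not be enough.* A reader might infer that a single Period 1 plot settles the matter. That holds only if the half is counted within Period 1. If plots are pooled over periods and arms, one is not enough. The SAP does not say, so the Period 1 rates are conditional on that count.

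*The rule might be safe once the concurrent correlation is moderate.* For a concurrent, decaying r=0.3, the above-lag-0 reading misfires in only 0.5-3% of trials at autocorrelation 0.4 to 0.65. But the rate is about 11% at 0.8 and 26% at 0.9, and 46-85% if the 0.02 plateau counts. The reassurance covers only part of the rule.

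**Conclusion.** The concern holds in this form: the text of SAP 8.1.1 gives no size for a bump or plateau, leaves the computed intervals out of the rule, and does not define which plots make up the half. When the true correlation is zero or flat, following the rule within Period 1 can produce a false lag conclusion in anything from about 1% to 98% of trials, depending on how the plot is read. That spread is itself the defect.

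The missing definitions can be read directly from the text. The percentages rest on the assumed autocorrelations, the assumed data model, complete data for 350 subjects and counting within Period 1; the plateau figures also depend on what Figure 2 shows. The consequence is limited to one exploratory statement. It should be fixed because the change is cheap and the statement answers part of a primary objective.

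**What to change.** In SAP 8.1.1 replace both interpretation bullets with:

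> Plots are shown with 95% CIs and are descriptive. For each plotted X and lag i > 0, rho(X, X+i) minus rho(X, X) is estimated on subjects with CFS at X and SANDE at X and X+i, with a subject-level bootstrap CI. For FAS Period 1, an exploratory statement of a lagged response is made only if the CI of at least one of the five contrasts, Bonferroni-adjusted, lies above 0. The same contrasts are presented descriptively for Period 2 by arm and for the Entire Study.

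The five contrasts are three from Month 3 and two from Month 6. A max-t interval is an acceptable equivalent. State that this is an exploratory, interval-based statement, consistent with Protocol 13.1.2 and an exception to the no-testing sentence in SAP section 5. Record the change in SAP section 10. The SAP describes the interim thus: "The purpose of the interim analysis is to present appropriate summary of data collected for the period 1". The documents do not say whether those results had been seen; if they had, label the rule post hoc.

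**What it gains.** With zero or flat correlation and n=300 to 350, Bonferroni-adjusted paired-difference intervals gave 2-3% false conclusions, and unadjusted intervals 10-12%. The adjusted version detected a true rise of 0.10 per visit (from 0.1, levelling off after two visits) in 96-100% of runs and a rise of 0.05 per visit in 40-67%.

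**What it costs.** SAP wording and a short bootstrap program; no new data. Subjects lacking the visits compared drop out of a contrast; their number is unknown. A lag is declared less often. In a max-t version that averaged the differences over X (n=300 assumed), a one-visit lag of r=0.1 was detected in only 3-18% of trials. A non-declaration must therefore not be read as evidence of no lag. Lags beyond 9 months are only described.

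**Minimum alternative.** Delete the second, concluding bullet and present the plots with their intervals as descriptive only.
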